## 1. BACKGROUND AND SIGNIFICANCE

Post-operative delirium (POD), commonly encountered after surgery, is an acute brain dysfunction characterized by disturbances in attention, awareness, and cognition not explained by a preexisting neurocognitive disorder. Although the increased mortality rates ascribed to delirium remain debatable, delirium remains a leading cause of preventable morbidity in hospitalized elderly patients. It is also associated with prolonged hospitalization, prolonged institutionalization, and long-term cognitive deficits. The total healthcare cost attributable to delirium is estimated between \$143 and \$152 billion annually. Thus, principled strategies to pre-emptively identify and target patients at risk for delirium may result in significantly improved peri-operative outcomes.

Sleep is a naturally occurring state of decreased arousal that is crucial for normal immune and cognitive function. Basic science and clinical studies suggest sleep disturbance as a modifiable risk factor for post-operative delirium (POD). Sleep deprivation, which is associated with increased pro-inflammatory cytokine levels including interleukin-6, precedes the onset of delirium in some patients. A recent investigation linking brain activity of microglia, astrocytes, interleukin-6 and delirium in humans, suggests a mechanistic link between sleep deprivation, brain inflammation and delirium. Further, conditions associated with delirium are characterized by activation of the inflammatory cascade with acute release of inflammatory mediators. Increasing age is a significant risk factor for the development of delirium. Notably, aging is associated with activated brain glia cells. Following a systemic challenge such as critical illness, these activated glia have been suggested to facilitate an exaggerated neuroinflammatory state that predisposes to delirium. Thus, as systemic inflammation may be involved in the pathophysiology of delirium, sleep disturbance may constitute a modifiable risk factor for POD. However, structured studies are necessary to make clear the extent to which this association exists and is modifiable.

## Systematic Literature Search

We conducted a systematic search into the association between sleep disturbance and POD. The search included patients across a range of surgical specialties. The aim of the search was to capture studies that assessed a history of sleep disturbance and POD. Published literature were searched using strategies devised by a librarian using a combination of standardized terms and keywords, and were implemented in Pubmed, Embase, CINAHL, Web of Science and Cochrane from inception until May 31st, 2017. We identified 1,238 citations (328 studies in the MEDLINE database (PubMed), 939 in EMBASE, 86 in CINAHL, 266 in Web of Science and 76 in the Cochrane Library Database), and included 12 unique studies enrolling 1,878 patients. The studies were methodologically diverse with respect to metrics that were used to diagnose sleep disturbance and POD.

# Search Methodology Summary

All studies were reported between 2001 and 2015. They included seven prospective cohort studies and five retrospective studies. Nine studies had a sample size greater than or equal to 60. The largest study was a retrospective cohort study involving 432 patients,  while the smallest was a prospective cohort study as a retrospective cohort study involving 432 patients,  while the smallest was a prospective cohort study with 40 patients. Four studies specified obstructive sleep apnea as the type of sleep disorder evaluated. However, the other studies did not explicitly specify the type of sleep disorder that was evaluated. Eight studies assessed pre-operative sleep disorder, three studies assessed sleep disorder occurring after the onset of delirium. Five studies evaluated orthopedic surgeries, four studies evaluated cardiac surgeries and others evaluated thoracic and non-cardiac surgeries. Eight studies utilized the Confusion Assessment Method (CAM), a standardized evidence-based tool,  to diagnose delirium; two studies used the Diagnosis and Statistical Manual of Mental Disorders (DSM-IV); and two studies utilized patient chart records and information obtained from caregivers to diagnose delirium. We excluded cross-sectional studies, case reports and studies not reported in English language.

#### **Pooled Analysis Summary**

A total of 1,199 patients and 244 cases of delirium were analyzed. We found that the pooled odds ratio for the association between sleep disturbance and POD was 5.24 (95% CI: 3.61 to 7.60, p <0.001; l=0.0%, p=0.76). The pooled odds ratio for the association between pre-delirium sleep disturbance and POD of 5.24 (95% CI: 3.61 to 7.60, p <0.001; I=0.0%, p=0.76; Fig 2b) was statistically significant. The odds ratio associated with obstructive sleep apnea and unspecified types of sleep disorder were 4.75 (95% CI: 2.65 to 8.54, p <0.001; I=0.0%, p=0.85), and 5.60 (95% CI: 3.46 to 9.07, p <0.001; l=0.0%, p=0.41), respectively. We conducted a sensitivity analysis using risk ratios obtained from the prospective studies,  and found that the pooled risk ratio for the association between sleep disturbance and POD of 2.90 (95% CI: 2.28 to 3.69, p <0.001; l=0.0%, p=0.89; Fig 5) was significant.

Figure 1. Pooled analysis of studies with crude odds ratio

Evans et al., in a pilot prospective study that used EEG recordings to objectively study predictors of POD, found that diminished sleep time and increased sleep latency on POD 1 is associated with increased incidence and severity of delirium. Sleep disturbance is a hallmark feature of the postoperative period, and results from this study do not resolve whether pre-existing sleep disturbance is associated with an increased incidence of POD. Other studies that have evaluated the association between sleep disorder and delirium have utilized measures such as wrist actigraphy or the Pittsburgh Sleep Quality Index (PSQI) to evaluate sleep disturbance. Unfortunately, the use of actigraphy or the PSQI in isolation do not provide accurate details on sleep quality or microstructure dynamics of sleep such as slow-delta oscillations, sleep spindles, K-complexes or REM alpha oscillations. These dynamics, which may aid the pre-emptive identification of patients that are prone to developing POD, can be obtained using a portable sleep polysomnography (PSG) device.

Therefore, we aim to study the association between preoperative sleep disturbance and POD. Our central hypothesis is that preexisting sleep dysfunction will correlate with incidence of POD. To enable assessment of objective sleep quality metrics, our cohort will be comprised of patients admitted to the hospital prior to surgical procedures. We will perform cognitive and delirium assessments, polysomnography and blood sample collection peri-operatively. Additionally, previous research has demonstrated a clear link between infection and sleep apnea. Thus, we will track subjects' postoperative infection rates in order to assess the generalizability of this outcome to sleep disturbance overall. At the conclusion of this study, we will have expanded our knowledge of the pathophysiology of POD.

#### 2. SPECIFIC AIMS

The specific aims of this study are:

## AIM 1: To use PSG and a validated sleep questionnaire to characterize sleep quality in POD patients Hypothesis 1.1. POD will be associated with significantly decreased pre-operative total sleep time

Hypothesis 1.2. POD will be associated with a pre-existing history of sleep disruption as measured by the Pittsburgh Sleep Quality Assessment (PSQI)

AIM 2: To use serum profiling to understand the association between POD and circadian disruption Hypothesis 2.1. POD will be associated with decreased am mRNA transcript levels of clock genes (Bmal1, Clock, Per1 and Per2).

### 3. Subject Selection

**Primary inclusion criteria for patients:** 1) age  $\geq$  60; 2) inpatient and scheduled for surgical procedure at MGH. **Primary exclusion criteria for patients:** 1) blindness, deafness or the inability to speak English; 2) inability to provide informed consent.

Primary objective drop for patients: 1) post-operative intubation >24 hours.

### 4. Subject Enrollment

**Recruitment:** This study will be performed at the Massachusetts General Hospital in Boston, MA. We will enroll 100 male and female patients into the study. Cardiac surgical patients and orthopedic trauma patients represent the primary surgical patients that are admitted to the hospital prior to their surgical procedures. Thus, we will screen cardiac and orthopedic surgical schedules to identify potential eligible subjects. We will engage members of the patient's clinical care team to ask the patient if he/she is willing to have a study team member approach him/her to discuss a research study. This initial care patient contact will be performed by cardiac or orthopedic clinical staff (M.D., P.A, N.P, R.N), cardiac or orthopedic anesthesia care providers (M.D., C.R.N.A, S.R.N.A), or hospital geriatric clinicians (M.D., P.A, or N.P). Study team members will only approach patients that are interested in learning more about the study. They will explain the details of the study and provide a flyer summarizing study procedures to the patient. Formal written consent will be obtained prior to any study related procedures.

**Retention**: All subjects who provide written consent but later decline participation in the study will not be subject to any study-related follow-up.

**Remuneration:** There will be no monetary remuneration for this study.

**Procedure for informed consent:** Members of the patient's clinical care team will briefly introduce the study to the patient. Study team members will only approach patients that are interested in learning more about the study. Study team members will explain the details of study and provide a flyer summarizing study procedures to the patient. If the study team member is a non-physician (i.e. clinical research coordinator), he/she will explicitly offer the patient an opportunity to speak to physician investigators. The study team member will review and discuss the details of the research study with the patient using the informed consent document as a guide. The discussion will include all the required elements of informed consent. A formal written consent will be obtained only after all questions and concerns have been addressed.

#### Treatment Assignment and Randomization: Not applicable.

#### 5. Study Design

Pre-operative Visit: We will obtain a written consent prior to conducting the Long-CAM, PSQI, Patient Health Questionnaire (PHQ-9), Trust in Physician Scale (TPS) and the abbreviated Montreal cognitive assessment. Next, we will place a portable PSG device at approximately 7 pm to record neurophysiological data using the Compumedics Portable PSG monitoring device. Due to clinical care concerns, patient acuity, patient unavailability and several other unforeseen factors, PSG may not be placed on all study subjects. A minimum of the following electrodes will be placed for sleep staging: Two central channels (C3 and C4), two electrooculogram channels to capture lateral eye movements, and two reference channels over the left and right mastoids.

Post-operative Day 0: PSG electrodes will be removed at approximately 6am. Additionally, we will obtain approximately 13ml of blood to be processed into mRNA to understand the association between peri-operative circadian cycle disruption of four circadian clock genes (Bmal1, Clock, Per1 and Per2) and POD. The PI will ensure that appropriate privacy and de-identification procedures are in place for the collection and storage of blood. All MGH ORs are equipped with a four-channel frontal EEG device (Sedline, Masimo, Irvine, CA). Thus, we will collect intraoperative routine EEG data that is recorded as part of routine anesthetic management. Due to clinical care concerns, patient acuity, Sedline electrode unavailability and several other unforeseen factors, blood and Sedline EEG data may not be obtained on all study subjects.

Post-operative Days 1-3: On post-operative day 1, we will obtain approximately 13ml of blood as a post-surgical measure of mRNA levels to understand the association between peri-operative circadian cycle disruption of four

circadian clock genes (Bmal1, Clock, Per1 and Per2) and POD. Delirium assessments may be conducted twice daily (AM and PM with at least 6 hours between tests) beginning on postoperative day 1 using the Long Confusion Assessment Method (CAM). PHQ-9 will be assessed on POD 3 only. Subjects who elect to withdraw from the study during their hospital stay will be re-approached by the study team within 8-24 hours of study withdrawal. The study team member will elicit the reason for study discontinuation and confirm the withdrawal decision. This visit serves to ensure that the withdrawal decision was made during an informed and non-delirious cognitive state. In the event that a subject finds it difficult to complete an assessment (i.e. pain, clinical intervention), only the long-CAM domains necessary to dispel the presence of delirium will be assessed (i.e. acute onset, inattention, disorganized thinking and altered level of consciousness). Subjects who cannot complete this shortened assessment will be re-approached several hours later. Long-CAM assessments for subjects who are reintubated for clinical care or for further surgical management will be considered missing data.

Post-operative Day 30: PHQ-9 and the Pain Interference 8a (PROMIS SF v1.0) questionnaires will be administered over the phone. Subjects' infection rates will also be tracked postoperatively.

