## 6. DATA ANALYSIS PLAN

Hypothesis tests will be performed using a two-sided significance level (type I error) of  $\alpha$ =0.05. Aim 1 (Hypotheses 1 and 2) outcome will be evaluated using binominal regression models with adaptive elastic net penalty to examine the association between total sleep time and POD. Patient characteristics of interest (i.e. age, gender, baseline cognitive score, pain, depression symptom score, frailty index, Charlson comorbidity index) will be included into this regression model. Because missing data rarely occur entirely at random, we will assess associations between patient characteristics with respect to missing data. If patients with at least one missing outcome value are different from those with complete outcomes data, we will use multiple imputation to assign values to missing data risk factors and outcomes in regression modeling. Aim 2 (Hypothesis 1) Wilcoxon rank-sum tests with corrections for multiple comparisons will be used to assess differences for each analyte or transcript. In other exploratory analysis, we will assess differences in the EEG (PSG and intraoperative) dynamics of delirious and non-delirious patients. To assess statistical significance for the difference in EEG spectra at each frequency, we will compute the 99% confidence interval of the median difference between groups by using an empirical bootstrap approach. The null hypothesis will be rejected only if the confidence interval of the median difference at each frequency exceeds the significance threshold over a contiguous frequency range  $\geq$  2W. We will also characterize differences in sleep microstructure dynamics (i.e. spindle power, spindle rate, spindle peak frequencies, slow-delta phase- spindle amplitude modulation) between groups using algorithms developed in-house.

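### Hypothesis 2.1 concerns morning clock-gene levels, but the plan sets no clock window for the day-1 draw, does not require draw times to be recorded, and uses a test that cannot adjust for them

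*Combined protocol and SAP*

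**What the plan says.** Section 2 states Hypothesis 2.1 as "POD will be associated with decreased am mRNA transcript levels of clock genes", for Bmal1, Clock, Per1 and Per2. The word *am* is the only time of day attached to the transcripts, and no sample day is named.

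Section 5 describes two blood draws.
- **Day 0.** "PSG electrodes will be removed at approximately 6am", and the next sentence begins "Additionally, we will obtain approximately 13ml of blood to be processed into mRNA". The draw has no clock time of its own.
- **Day 1.** "On post-operative day 1, we will obtain approximately 13ml of blood as a post-surgical measure of mRNA levels". Only the day is given.

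Elsewhere the same section does set times of day. The delirium assessments get them: "Delirium assessments may be conducted twice daily (AM and PM with at least 6 hours between tests) beginning on postoperative day 1". Nothing says that the time of either draw is to be recorded. Section 5 also warns that "blood and Sedline EEG data may not be obtained on all study subjects".

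Section 6 gives the Aim 2 analysis in one sentence: "Wilcoxon rank-sum tests with corrections for multiple comparisons will be used to assess differences for each analyte or transcript". The patient characteristics listed there belong to the Aim 1 regression, and draw time is not among them.

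**The concern.** Clock-gene expression is studied here because it follows the time of day. Two samples taken some hours apart can differ even when the patients do not, so draw time has to be held fixed or modelled. The plan implies the first through one word in the hypothesis and provides for neither in the procedure or the analysis.

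There are two possible consequences. If draw times vary in the same way in both groups, they add noise to a comparison with about 13 delirious patients. If they differ between the groups, the rank-sum test attributes the time-of-day difference to delirium, and this can create a finding or hide a real one. A draw time that was never recorded cannot be recovered at analysis, so nobody could tell afterwards which of these had happened.

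**Working it through.** **The plan's own figure.** Section 7 sizes the study for total sleep time: difference 60 min, SD 60 min, two-sided alpha 0.05, power 0.90, allocation ratio 78/13 = 6. Then n = (1 + 1/6) × (1.960 + 1.282)² × (60/60)² = 12.3, rounded up to 13, and 6 × 13 = 78. The figure reproduces and is not in dispute. No sample size is given for Aim 2, so 13 v 78 is borrowed for illustration.

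**Assumptions not in the documents.** Log expression is A·cos(2πt/24) plus standard normal noise, where t is hours from the peak and A is 0.5, 1 or 1.5 between-patient SD. Per-gene alpha is 0.05/4 = 0.0125 (Bonferroni over four genes; the plan does not name its correction).

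**Case 1: draw times differ by group, no true difference.** Each group is drawn in a 2-hour uniform window, and the delirious group's window is centred 2 hours later. Averaging over the window multiplies the cosine by sin(0.262)/0.262 = 0.989.
- Others centred on the peak: difference = A × (1 − cos 30°) × 0.989 = 0.132A.
- Others centred on the steepest point (6 h from peak): difference = A × (cos 90° − cos 120°) × 0.989 = 0.494A.

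The standard error of a group difference is √(1/13 + 1/78) = 0.300 SD. The spurious difference is therefore 0.44A standard errors near the peak and 1.65A at the steepest phase, against a critical value of 2.50.

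**Case 2: same 6-hour window in both groups, true 1-SD difference.** Draw time adds variance. Over ±3 h (±π/4) this is (0.5 − 1/π)A² = 0.18A² at the steepest phase, and (0.5 + 1/π − 0.900²)A² = 0.008A² at the peak.

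Simulated rank-sum results:

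| | A = 0.5 | A = 1 | A = 1.5 |
|---|---|---|---|
| False positives, 2-h shift, near peak | 0.015 | 0.02 | 0.03 |
| False positives, 2-h shift, steepest phase | 0.04 | 0.17 | 0.40 |
| Power, common 6-h window, near peak | 0.73 | 0.73 | 0.73 |
| Power, common 6-h window, steepest phase | 0.72 | 0.65 | 0.54 |

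The power reference, with no spread in draw time, is about 0.73. The first cell varied from 0.012 to 0.015 between runs and is practically nominal.

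**A shift within the morning.** With delirious patients drawn 09:00–12:00, the others 06:00–09:00, and peaks at 02:00, 08:00 or 14:00, the type I error at alpha 0.05 is 0.06 to 0.22 (A = 0.5) or 0.09 to 0.62 (A = 1). At alpha 0.0125 it still reaches 0.085 or 0.38. When the rhythm works against the hypothesis, power for a true 1-SD decrease (alpha 0.05) falls from about 0.89 to 0.53 or 0.14.

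**Timing unrelated to delirium.** With the same 06:00–18:00 window in both groups, type I error stays at 0.049 to 0.052 at alpha 0.05.

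**Does the remedy work?** A common 05:00–07:00 window gives type I error of 0.048 to 0.054 at alpha 0.05. A linear regression with sine and cosine terms for draw time gives 0.010 to 0.016 against 0.0125. Adjustment cannot replace the common window, however. In Case 1 the two windows only touch. The variance of draw time between groups is (13 × 78/91²) × 2² = 0.490 and within groups 2²/12 = 0.333, so a single linear time term explains 0.490/0.823 = 0.595 of group membership. The standard error of the delirium effect then rises by a factor √(1/0.405) = 1.57.

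**The case against.** The strongest reply is that *am* already settles the matter: morning samples are intended, and Section 5 merely does not repeat it. This stands to a degree. A reader might infer that the day-1 sample may be drawn at any hour, but that goes against the plan's own hypothesis. What remains is that a morning is not a clock window, and a shift within it can be enough to matter.

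A reader might also infer that day 1 is the sample that tests Hypothesis 2.1. No section says so. If day 0 is the test sample, the problem shrinks: that draw is described beside the 6am electrode removal and before the intraoperative EEG, and postoperative delirium assessment starts on day 1, so delirium itself could hardly move it.

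Thirdly, a reader might infer that delirious patients will be drawn at other hours. The documents do not show this. The text on re-approaching subjects several hours later concerns the delirium assessment, and patient acuity is given as a reason for blood being missing, not late. The bias is therefore conditional.

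Finally, phase decides the size. Near the peak, a 2-hour shift does almost nothing. No single false-positive rate can be quoted, only the range.

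**Conclusion.** The concern holds as a gap in procedure and analysis: an implied morning draw without a window, no requirement to record the time, no named test sample, and a test that takes no covariate. With timing unrelated to delirium, the cost is power: none to speak of near the peak, and a fall from about 0.73 to between 0.72 and 0.54 at the steepest phase for a common 6-hour window. With a 2-hour difference between groups, the false-positive rate per gene runs from practically nominal to about 0.40 against 0.0125. A multiplicity correction lowers these rates but does not remove the bias. Amplitude, phase, windows and shifts are all assumptions, and 13 v 78 may be optimistic because blood may be missing. The point bears on Aim 2 only and should be addressed before samples are collected; the primary sleep-time objective is unaffected.

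**What to change.** In Section 5, carry *am* into both research draws as one common morning clock window, chosen by the investigators, and require the actual draw time to be recorded for every sample.

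In Section 2 or 6, state whether the day-0 or the day-1 sample tests Hypothesis 2.1.

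In Section 6, test Hypothesis 2.1 with a regression of log or rank expression on delirium status that includes draw time, for example as sine and cosine terms. Keep all samples with a recorded time, and repeat the analysis on in-window samples as a sensitivity analysis. Report draw times by group. The adjustment assumes the same rhythm in both groups, which is uncertain in a study of circadian disruption, and it is weak when draw times barely overlap. The common window therefore does most of the work.

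The cost is one time stamp per sample and one or two covariate terms, to be borne with about 13 cases. No extra blood is needed, and no sample with a recorded time is dropped from the main test.
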